6.3 Remote Telephone/Video Visits

Multiple visits will occur through videoconference (preferred) or telephone to assess for adverse events and ensure compliance with medication adherence. These visits will occur at the following timepoints: 2 day post procedure and 1, 2, 6, 10, 14, 18, & 22 weeks post procedure.

A final remote telephone/video visit will occur 1 week following the final on-site study visit to assess if there is any clinical change following discontinuation of study treatment.

6.4 Visits 3 & 4

These visits will be identical to visits 1 and 2, with the exception that study drug will be returned at the final on-site study visit.

Page 16 of 34

Test Schedule

Study Activity	V	isit 1	Visit 2	Visit 3	Visit 4
	Screen	Procedure	1-7 days following Visit 1 or 1 day prior to Visit 1	Week 24 (+/- 2 weeks)	1-7 days following Visit 3, or 1 day prior to Visit 3
Informed consent ¹	X		X		
History	X				
Concurrent meds	X		X	X	X
Physical exam (Ht, Wt, BSA, VS)	X			X	
Adverse event evaluation		X	X	X	X
NYHA Classification	X			X	
Blood Draw	X^2	X^3		X^1	
Serum pregnancy ⁴	X		X	X	
RHC		X		X	
Exercise study with hemodynamics		X		Х	
Blood gasses		X		X	
Limited Echo		X		X	
Blood volume test			X		X
SF-36 Questionnaire			X		X
DEXA			X		X

¹ Consent can occur on Visit 1 or Visit 2 and must occur before any research activities take place.

Page 17 of 34

² Pre-procedure: CBC, creatinine, BUN, sodium, potassium, aspartate aminotransferase, alanine aminotransferase, total, direct and indirect bilirubin, hsCRP, NTproBNP, and HgbA1c as part of clinical care

³ Research blood will be drawn, processed, stored and tested in [name] lab.

⁴ For women of childbearing potential, required to be done once before any research assessments, either Visit 1 or Visit 2.

DAPA/Placebo	X^5	X^5	X^6	X^6

⁵ 12 week supply dispensed once Visit 1 and Visit 2 are complete and 12 week supply mailed to patient at 12 weeks after remote visit

⁶ Study drug returned at either Visit 3 or 4, whichever is later

7 Statistical Plan

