3.1 General Description

This is a mechanistic phase II placebo-controlled trial designed to determine whether treatment with dapagliflozin for 6 months will improve exercise hemodynamics, cardiac metabolism, and clinically relevant endpoints in patients with HFpEF.

Brief Synopsis of Methods:

- 1) Enroll subjects with HFpEF. Some patients will have previously been identified and some will have be referred to the catheterization lab for evaluation of dyspnea and suspected HFpEF. The latter patients will only qualify for randomization if they meet hemodynamic entry criteria for HFpEF (PCWP of ≥25 mmHg with exercise).
- 2) Safety lab sampling (complete blood count, creatinine, blood urea nitrogen, sodium, potassium, aspartate aminotransferase, alanine aminotransferase, total, direct and indirect bilirubin) hs-CRP, HgA1c, NTproBNP will be performed. Values may be used up to a week prior to study if the same bloods have already been drawn.
- In the preparation area, an IV cannula will be inserted in a forearm vein for initiation of isotope infusion ([U-13C] palmitate), allowing for attainment of steady-state prior to transfer to the catheterization laboratory (~60 min). Isotope infusions will be continued until blood sampling studies have been completed.
- 4) Assess hemodynamics at rest and during exercise using gold standard invasive techniques in patients with HFpEF. Venous, arterial and coronary sinus blood samples obtained at rest and during exercise. Focused echocardiography examination with measurement of LV and RV tissue Doppler echocardiography and cardiac volumes will be performed. This will conclude the invasive catheterization visit. The patient will be monitored per standard clinical protocols following right heart catheterization and discharged the same day.
- At a separate visit following cardiac catheterization, but prior to receipt of study drug, participants will have a QOL assessment, dual energy X-ray absorptiometry (DEXA), and measurement of plasma volume using the labelled albumin indicator dilution technique. Study coordinator will review patient preferences regarding contact during the study including video teleconference (preferred) or phone call.
- Patients will be randomized in a double-blind fashion to dapagliflozin 10 mg once daily or matching placebo. Study drug dispensed by research pharmacy.

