- Telephone visits will be conducted at 2 days, 1 week, 2 weeks, and then every 4 weeks thereafter, for a total of 24 weeks. One week after visit 4, there will be an additional telephone visit for safety after patient is no longer on study drug. All phone visits will have a window of +/- 3 days. Participants will be contacted by phone or through videoconference visits (based upon patient preference) to evaluate for AEs/SAEs, and encourage compliance with the study medication. Adverse events will be determined using a general approach, asking participants if there have been any changes to their overall health since the prior visit, including any unplanned hospital

Page 9 of 34

- or clinic visits. At 2 weeks, as part of standard of care, patients will undergo laboratory draw from complete blood count, electrolytes and renal function at their local lab, with results reviewed by the study teamIf needed, a physician on the trial can put in a referral order for the lab work.
- At the conclusion the 24 week treatment period, participants will return to complete the same invasive hemodynamic assessments and noninvasive assessments as described in steps (1) through (5) above (2 visits). Patient must remain on study drug through Visit 4, and may be on drug up to 7 days after the 24 week mark.
- 9) A follow up telephone/videoconference visit will be scheduled 1 week after completion of the trial to evaluate for AEs/SAEs following completion. This will have a window of +/- 3 days.

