After resting hemodynamic assessments have been performed, a 6 Fr MPA catheter will be advanced from the right internal jugular vein to the coronary sinus (CS) under fluoroscopic guidance, with CS location confirmed by oximetry (O₂ saturation<45%). Blood samples from the radial artery and CS will be drawn in triplicate (3 ml each) and averaged to measure blood gases (trans-myocardial O₂ uptake and CO₂ release based upon the difference between artery and CS tensions) along with glucose, lactate, triglyceride, pyruvate, ketone, and FFA uptake (total FFA and [U-¹³C]palmitate – enrichment in arterial and CS blood)). Additional mandatory research blood samples will be drawn frozen and stored for future discovery analysis. Samples will come from the CS, vein and artery once at the beginning of the procedure for future research. Samples will be transferred in iced tubes, centrifuged at 4°C and stored at -80°C for analysis.

Following resting metabolic assessments, participants will exercise at 20W workload on a supine ergometer for 3 minutes with the CS catheter in place, after which time arterial and CS sampling will be repeated during exercise in the same manner as at rest. The MPA catheter is then removed from the CS and exercise hemodynamic measurements are obtained. After obtaining exercise hemodynamic data at the 20W workload, workload is

increased in 20 W stages (3 minutes each) to volitional exhaustion. Hemodynamics and arterial and mixed venous blood samples are obtained at each stage.

Following exercise, catheters are removed and the patient is observed in the recovery area as per standard clinical practice prior to discharge.

6.2 Visit 2

At a second visit, typically the following day from the invasive catheterization can occur the day before visit 1 to allow flexibility, but no later than one week later, the patient will undergo plasma volume and blood volume assessment using the radiolabeled iodinated albumin ($^{131}\text{I},\,5{-}25~\mu\text{Cu}$) indicator dilution technique (BVA-100 Blood Volume Analyzer, Daxor Corp, NY) as is used clinically at Mayo Clinic and as we have described. 16 Patients will also undergo a DEXA scan in the Mayo CRTU.

At this visit QOL will be assessed using the SF-36 Questionnaire. Participants will receive the first 12 week supply of study drug as allocated in the randomization, and review study procedures and preferences for remote visits throughout the study period.

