8.4 Pregnancy

All pregnancies must be reported to AstraZeneca. The Pregnancy and breast-feeding exclusion criterion should be used in combination with the discontinuation criterion for pregnancy If a patient becomes pregnant during the course of the study, investigational product should be discontinued immediately and an AZ representative notified. Pregnancy itself is not regarded as an AE unless there is a suspicion that the investigational product under study may have interfered with the effectiveness of a contraceptive medication. The outcome of all pregnancies (spontaneous miscarriage, elective termination, ectopic pregnancy, normal birth or congenital abnormality) should be followed up and documented, even if the patient was discontinued from the study.

All pregnancies and outcomes of pregnancy should be reported to AstraZeneca's designated fax line: [contact] or email:

[contact]

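### The baseline rule that a pregnancy test precedes research procedures is not repeated at follow-up, so I-131 albumin and DEXA at an early Visit 4 can come before the follow-up test

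*Combined protocol and SAP*

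**What the plan says.** **Visit order.** Section 6.2 describes Visit 2 as "typically the following day from the invasive catheterization can occur the day before visit 1 to allow flexibility". Step 5 of the synopsis in Section 3.1 puts the non-invasive assessments "At a separate visit following cardiac catheterization, but prior to receipt of study drug", so catheterization first is the usual order, and the week 24 step of that synopsis repeats steps 1 to 5. The Test Schedule gives Visit 4 the same freedom relative to Visit 3: "1-7 days following Visit 3, or 1 day prior to Visit 3". Footnote 6 to the table has study drug handed back at the later of the two visits, so the authors foresaw Visit 3 coming last.

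**Radiation procedures.** At Visit 2, Section 6.2 says, "the patient will undergo plasma volume and blood volume assessment using the radiolabeled iodinated albumin", and a DEXA scan is done. The table marks both procedures again at Visit 4.

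**Pregnancy test.** The serum pregnancy row is marked at screening (Visit 1), Visit 2 and Visit 3, and is blank at Visit 4. Footnote 4 reads: "For women of childbearing potential, required to be done once before any research assessments, either Visit 1 or Visit 2". The narrative mentions the test in Section 6.1 (Visit 1) and not in Section 6.2 (Visit 2).

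**Link between baseline and follow-up.** Section 6.4 says: "These visits will be identical to visits 1 and 2, with the exception that study drug will be returned".

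**Pregnancy during the trial.** Section 4.2, item 10, excludes women of childbearing potential who will not use accepted contraception. Section 8.4 still provides for the event: "If a patient becomes pregnant during the course of the study, investigational product should be discontinued immediately".

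**The concern.** At baseline the plan allows either visit order and protects both. The test is marked in both columns, and footnote 4 puts it ahead of all research assessments. At follow-up the plan keeps the flexible order but not the protection: the test is marked only at Visit 3, and footnote 4 does not name Visits 3 or 4.

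A follow-up test has a protective purpose only if it comes before the exposure. In one permitted order it need not do so. At stake is avoidable fetal exposure to a research radioisotope and scan, in a woman who became pregnant during about six months of treatment and does not yet know it. This is a point about participant safety and has no bearing on the treatment comparison.

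**Working it through.** The plan gives no figure to reproduce. The check traces the permitted visit orders, then works out the age of the last required test and the likely number of women affected.

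**1. Permitted orders.** The inputs are the Test Schedule windows, marks and footnote 4. The columns are read as extracted from the PDF; their alignment agrees with the other rows.

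| Period | Order | Marked test relative to I-131 and DEXA | Is a test before them required? |
|---|---|---|---|
| Baseline | Visit 1 first | 1 to 7 days before | Yes, footnote 4 |
| Baseline | Visit 2 first | Same visit, before | Yes, mark at Visit 2 and footnote 4 |
| Follow-up | Visit 3 first | 1 to 7 days before | Yes in effect, by the mark at Visit 3 |
| Follow-up | Visit 4 first | 1 day after, if taken on the day of Visit 3 | No |

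Only the last row lacks a required earlier test. The remote contacts do not fill the gap, because none includes a pregnancy test. The week 2 local blood draw covers blood count, electrolytes and renal function only.

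**2. Age of the last required test at a reversed Visit 4.** Visit 3 falls at week 24, plus or minus 2 weeks:

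- Earliest: 22 × 7 = 154 days; less 1 day = 153 days (153 / 7 = 21.9 weeks).
- Latest: 26 × 7 = 182 days; less 1 day = 181 days (181 / 7 = 25.9 weeks).

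The last required test is therefore about 22 to 26 weeks old. This ignores the spread of up to 7 days between Visits 1 and 2.

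**3. Expected number of avoidable exposures.** A woman who is not pregnant would test negative and have the same dose and scan, so nothing is avoidable for her. The number is therefore

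N × (share of childbearing potential) × (share with Visit 4 first) × (share pregnant at week 24).

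N is 46 randomized or 41 completing (Section 3.2). The documents give none of the three shares. The assumed ranges are 0 to 10%, 0 to 50% and 0 to 5%.

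| Case | Calculation | Result |
|---|---|---|
| Lower bound | any share at 0 | 0 |
| Middle | 46 × 0.05 × 0.25 × 0.025 | 0.014 |
| Reversal in at most 25% | 46 × 0.10 × 0.25 × 0.05 | 0.058 |
| All ceilings, completers | 41 × 0.10 × 0.50 × 0.05 | 0.10 |
| All ceilings, randomized | 46 × 0.10 × 0.50 × 0.05 | 0.115 |

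The 25% row reflects Section 6.2, which calls the other order typical. The 5% ceiling makes no allowance for the contraception criterion, so the upper figures are generous.

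**The case against.** **The test may already come earlier.** Section 6.1 lets the routine bloods be drawn up to 7 days before catheterization, and the same awkward sentence mentions the pregnancy test. Carried forward by Section 6.4, this could allow the Visit 3 test to be drawn before a Visit 4 held the day before. That reading is reasonable, so one should not infer that staff who follow the table in the reversed order will necessarily irradiate before testing. What remains is that the safe order is allowed and not required.

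**Section 6.4 and the table.** A reader might infer that text and table contradict each other, because Section 6.4 calls the visits identical while Visit 4 lacks the mark that Visit 2 has. The documents do not support this. Section 6.1 lists the test at Visit 1 and Section 6.2 lists none, so carrying them forward gives a test at Visit 3 only, which is what the table shows. The test-first rule stands only in footnote 4, which is confined to baseline. The word is also used loosely: consent is marked at Visit 2 but not at Visit 4, and history at screening but not at Visit 3.

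**Rarity and other safeguards.** Catheterization first is the usual order, contraception is an entry condition, eight remote contacts take place during treatment, and Section 8.4 governs known pregnancies. All of this stands and keeps the expected number very low. None of it detects an unrecognized pregnancy before an early Visit 4. The sponsor evidently did not rely on contraception alone, since it schedules a test at Visit 3.

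**Conclusion.** The point holds as a narrow scheduling gap of the lowest severity. In one permitted follow-up order, no mark or footnote requires a pregnancy test before the I-131 dose and DEXA, and the last required test is then 153 to 181 days old. The gap concerns only women of childbearing potential whose Visit 4 comes first, and harm is avoidable only for one who is pregnant at that time. The expected number is 0 to 0.115 patients, or at most 0.058 if no more than a quarter of Visit 4s come first. Those figures rest wholly on assumed shares; the gap itself rests only on the Test Schedule and its footnotes. The primary endpoint, the analysis and the power are not affected.

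**What to change.** Mark serum pregnancy at Visit 4 as well as at Visit 3 in the Test Schedule, and extend footnote 4 with: *and once before any follow-up research assessment (Visit 3 or Visit 4, whichever comes first)*. This repeats the plan's own baseline pattern of two marks and one required test. It also states the order within Visit 3, where the coronary sinus catheter is placed under fluoroscopy.

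The cost is one table mark and one clause. No test is added. When Visit 4 comes first, the single follow-up test moves about one day earlier, and its result must be ready before that visit begins.

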7.1 Introduction to the Statistical Design

This study will use a 1:1 randomization to active therapy or control. The control group is scientifically necessary because it is expected that there will be longitudinal changes in cardiac function and hemodynamics in the absence of intervention that need to be accounted for in the analysis. The primary endpoint is left ventricular filling pressure, specifically pulmonary capillary wedge pressure (PCWP) measured invasively in the cardiac catheterization lab. Within each endpoint assessment period (described in section 6), a baseline (resting) and exercise assessment of PCWP will be gathered. The analysis plan described below will detail how the longitudinal measurements will be used to objectively test for differences both within group over time and between groups over time.

7.2 Randomization and Blinding

Scientific rigor is enhanced by randomization and blinding. Mayo Research Pharmacy will be provided a block randomization sequence that will be used by pharmacy to randomize enrolled subjects 1:1. Medical staff and patients will be both blinded about the randomization to achieve the most unbiased results.

7.3 Data Management Plan

The data will be secured in a central registry using REDCap. The principle investigator will be responsible for proper data quality assurance (data matching, source verification, and deidentification). Data will be stored on password protected computers with access only allowed to the investigators. The investigator will maintain records and essential documents related to the conduct of the study. These will include subject case histories and regulatory documents.

The investigator will retain the specified records and reports during the study and for a period of 2 years after the latter of the following two dates: The date on which the investigation is terminated or completed, or the date that the records are no longer required for purposes of supporting a premarket approval application or a notice of completion of a product development protocol.

7.4 Outcomes

The complete list of primary and secondary outcome measures is provided in the Outcomes section of the application (section 3.4-3.5). The primary outcome measure for this mechanistic trial is the PCWP assessed at baseline and 6 months after treatment under rest and exercise within the same catheterization session.

7.5 Sample Size Estimation

Based on preliminary data from our previous studies (Borlaug et al 2015, 2016), we know the PCWP is positively correlated within individuals between rest and exercise. Furthermore, the standard deviation of PCWP has been consistently ~5 mmHg, with some proportionality to the mean (i.e., more variability in those with pulmonary hypertension). To initially frame the sample size, we first focus on the exercise PCWP. We expect little, if

Page 19 of 34

any, improvement in PCWP in the control group (some improvement possible due to the Hawthorn effect). We assume the average exercise PCWP in obese HFpEF patients is 30 mmHg and expect a 20% (6 mmHg) reduction in exercise PCWP in patients treated with DAPA compared with patients with placebo. The test-retest variability in exercise PCWP is <5 mmHg.

Based on two sample t test, 36 patients (18 receiving DAPA and 18 placebo) would provide 93% power to detect a difference of 6mmHG or greater in PCWP during exercise workloads between the DAPA and placebo groups, with a common standard deviation of 5 mmHg, at 0.05 significance level. By including resting values of PCWP in the mixed model with repeated measures, this is expected to increase the power further.

7.6 Primary Analysis

The primary analysis will be conducted using a mixed model using all available data. There will be main effects and interactions used to classify the PCWP as of randomized treatment DAPA/control, exercise yes/no, and baseline yes/no. A random subject effect will be utilized to block data on individual participant. The model configured this way provided the means to conduct a likelihood ratio test for the importance of DAPA on altering the PCWP profiles as the test for the primary hypothesis. Statistical contrasts will be utilized to compare PCWP under exercise at the end of the treatment period between groups and the differences in the change in PCWP over the study period between groups. These two hypotheses are a priori specified and will not be adjusted for multiple comparisons as they are intrinsically linked to the primary likelihood ratio test. This statistical model does not per se adjust for measured covariates as fixed effects in the model. The model, however, does include the random effect that effectively "adjusts for baseline" using a random variance term. However, it is acknowledged while the design is randomized, the sample size is relatively small to rely on the large sample balancing properties of randomization to account for all confounding in the study. To this end, we will compute standardized differences for all putative confounding variables captured at baseline prior to randomization. Absolute values for the standardized mean differences (SMD) <10% will be considered support for "balance" between the groups. If there are plausible confounding variables with SMD > 10%, sensitivity analyses will be conducted using standard covariate adjustment methods including propensity score analysis. The propensity score analysis is to help mitigate the number of estimated parameters in the mixed model to help ensure convergence of the estimation process.

For the more general patient reported outcomes and other clinical assessment that have >2 replications, we will use a more generalized modeling framework that accounts for the actual time from baseline in the repeated measures model. Time varying covariates (e.g., marking the period of bariatric surgery) will also be considered to provide a model framework for the data over time. As with the primary analysis, the treatment group by time interaction terms will serve as the main statistical tests of the treatment effect. As with the primary analysis, additional adjustment for imbalance that was not controlled via randomization will be implemented.

Missing data occur. We will conduct sensitivity analyses using modern machine learning based imputation approaches including chained equations and random forest imputation. Differences in estimates between the imputed and the observed data will be examined through pattern mixture models. Lack of consistency of results may indicate an internal bias, so therefore we will disclose our findings by reporting data analysis under the various data imputation strategies.

Reproducible research principles will be integrated throughout the statistical analysis process. The two primary statistical languages of SAS and R will be utilized. In both cases, version controlled datasets will be utilized for any formal statistical reports. Programming code will be written such that all derivations and assumptions are documented within the source code and accompanying materials (i.e., no human manipulation of raw data values once entered into the master REDCap database). R markdown reports are the preferred study report formats as they allow for each communication of interpretation, raw numeric results and figures/tables.

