	15 1	APPENDIX I SHORT FORM 36 (SF-36) OUESTIONNAIRE	FREOR! BOOKMARK NOT DEFINED

LIST OF ABBREVIATIONS

AE Adverse Event/Adverse Experience

CFR Code of Federal Regulations

CRF Case Report Form DAPA Dapagliflozin

DEXA
Dual Energy X-ray Absorptiometry
DSMP
Data and Safety Monitoring Plan
FDA
Food and Drug Administration

GCP Good Clinical Practice

HFpEF Heart Failure with Preserved Ejection Fraction
HFrEF Heart Failure with Reduced Ejection Fraction
HIPAA Health Insurance Portability and Accountability Act

IB Investigator's Brochure

IND Investigational New Drug Application

IRB Institutional Review Board NYHA New York Heart Association

PCWP Pulmonary Capillary Wedge Pressure

PHI Protected Health Information

PI Principal Investigator

SAE Serious Adverse Event/Serious Adverse Experience

SF-36 Short Form 36 Questionnaire

Study Summary

Title	Evaluation of the Cardiac and Metabolic Effects of Dapagliflozin in Heart Failure with preserved Ejection Fraction (CAMEO-DAPA): A Phase II, Prospective, Double-Blind Study				
Running Title	CAMEO-DAPA				
Protocol Number	20-005646				
Phase	Phase II				
Methodology	Randomized, double blind placebo control				
Overall Study Duration	24 months				
Subject Participation Duration	Approximately 7 months				
Single or Multi-Site	Single				
Objectives	To determine whether treatment with DAPA for 6 months will improve pulmonary capillary wedge pressure (PCWP) at rest and during exercise in HFpEF and improve cardiac metabolism.				
Number of Subjects	Up to 41 Subjects fully completing trial, up to 46 accrual, to account for dropouts				
Diagnosis and Main Inclusion Criteria	HFpEF subjects with obesity defined by clinical symptoms of HF: Dyspnea (NYHA II-IV without cardiac or ischemia explanation), EF ≥ 50%				
Study Product, Dose, Route, Regimen	Dapagliflozin (DAPA) 10 mg once daily versus matching placebo				
Duration of Administration	6 months				
Reference therapy	Placebo				
Statistical Methodology	The principal comparisons will be a comparison of pulmonary capillary wedge pressure incorporating values measured at rest and during exercise using mixed effects model analysis of covariance.				

1 Introduction

This document is a protocol for a human research study. This study will be carried out in accordance with the applicable United States government regulations and Mayo Clinic research policies and procedures.

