3.4 Primary Study Endpoints

The primary endpoint will be the PCWP incorporating values at rest, with feet elevated, and at 20 Watts exercise after treatment with study drug for 6 months relative to the respective PCWP values at each stage in the initial assessment prior to study drug. This will be analyzed using a mixed model with repeated measures (MMRM).

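### The primary PCWP analysis is described in three ways that do not agree, and section 7.6 read literally cannot analyse the three-stage endpoint of 3.4 or adjust its exercise contrast for baseline

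*Combined protocol and SAP*

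**What the plan says.** - **Study Summary:** the comparison is of PCWP "incorporating values measured at rest and during exercise using mixed effects model analysis of covariance".
- **Section 3.4:** "The primary endpoint will be the PCWP incorporating values at rest, with feet elevated, and at 20 Watts exercise after treatment with study drug", each stage taken relative to its own pre-drug value and analysed by an MMRM.
- **Section 7.6, primary analysis paragraph:** "The primary analysis will be conducted using a mixed model using all available data". The fixed factors, with interactions, are "randomized treatment DAPA/control, exercise yes/no, and baseline yes/no". Then: "A random subject effect will be utilized to block data on individual participant". And: "This statistical model does not per se adjust for measured covariates as fixed effects in the model". The same paragraph says the random effect in substance adjusts for baseline. The primary test is a likelihood ratio test (LRT) of whether dapagliflozin alters the PCWP profiles. Two unadjusted contrasts follow: exercise PCWP at end of treatment, and "the differences in the change in PCWP over the study period between groups".
- **Section 7.6, later paragraph on patient-reported outcomes:** by reference back to the primary analysis, it indicates that treatment-by-time interaction terms carry the test of treatment.
- **Sections 7.1 and 7.4:** only rest and exercise are mentioned; 7.4 refers to 3.4 for the outcome definition.
- **Section 7.5:** the SD is about 5 mmHg and tends to grow with the mean; rest and exercise values are positively correlated.

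**The concern.** Two of the differences are substantive.

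1. **Stages.** Section 3.4 has three and 7.6 has two. Nothing says whether the feet-elevated value is dropped, joined to rest or joined to exercise.
2. **Baseline.** In an analysis of covariance, baseline is a covariate. In 7.6 it is a level of the response, with no covariate in the model. These are different estimators.

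Section 7.6 also leaves open the residual covariance, the degrees of freedom, and whether the change contrast is at exercise or averaged over stages. Its primary-analysis paragraph does not name the terms the LRT drops. Two statisticians following the documents could therefore report different estimates and p-values, and could settle the choice after seeing data. The trial would also forgo precision available from baseline values it already collects.

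**Working it through.** **Plan's own figure (7.5).** Two-sample t test, 18 vs 18, difference 6, SD 5: SE = 5 × √(2/18) = 1.667, noncentrality 3.6, 34 df, two-sided 5%. Power is 93.8%, against the stated 93%. The figure reproduces, but it is for a t test on exercise PCWP alone and not for the 7.6 model.

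**Stage coding.** Assume effects of −2, −4 and −6 mmHg at rest, feet elevated and 20 W. If feet elevated is coded as rest, the 'exercise' effect is −6. If it is coded as exercise, it is (−4 − 6)/2 = −5. The estimand depends on a choice the plan does not make.

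**Baseline.** With treatment, exercise and baseline fully crossed and complete data, the end-of-treatment exercise contrast is the raw difference of two cell means. The random intercept changes its standard error and not its value, so it does not correct for baseline imbalance.

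**Error rates if 7.6 is fitted as a random-intercept model.** This model imposes equal variances and equal correlations. Inputs: two stages, 20 vs 21 completers (41, Study Summary). All variance shares below are assumptions. Approximation: rejection = 2[1 − Φ(1.96 √(V_model/V_true))].

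- *SD 4 at rest, 6 at exercise; end-of-treatment exercise contrast.* V_model = (16 + 36)/2 = 26; V_true = 36. Result 9.6%.
- *Equal SDs, 30% session share* (subject 0.4, session 0.3, residual 0.3). Of the six pairs among four values, two share a visit (correlation 0.7) and four do not (0.4). The mean is (2 × 0.7 + 4 × 0.4)/6 = 0.5, so the model residual is 0.5.
  - Stage-averaged change: V_model = 0.5; V_true = 2 × 0.3 + 0.3 = 0.9. Result 14.4%.
  - Exercise change: V_model = 1.0; V_true = 2 × (0.3 + 0.3) = 1.2. Result 7.4%.
- *Equal SDs, 30% subject-by-stage share* (0.4, 0.3, 0.3). The model residual is again 0.5. Exercise change: V_model = 1.0; V_true = 2 × 0.3 = 0.6. Result 1.1%.

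Simulation (40,000 null runs per pattern, nominal 5%) agrees:

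| Assumed truth | Test | Rejection |
|---|---|---|
| Equal SDs, equal correlation | contrasts | 4.9–5.0% |
| same | LRT, 2 df / 4 df | 5.7% / 6.0% |
| SDs 4/6 | end-of-treatment exercise | 9.5–9.6% |
| 30% session share | stage-averaged change | 14.8% |
| same | exercise change | 7.5% |
| same | LRT, 2 df | 9.8% |
| 30% subject-by-stage share | change contrasts | 1.1–1.3% |
| same | LRT, 2 df | 1.0% |
| Equal SDs and SDs 4/6, all correlation patterns | LRT, 4 df | 6.0–8.1% |

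The 2-df test is on the treatment-by-time terms. The 4-df test is on all treatment terms.

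**Power for a 3 mmHg exercise effect** (SD 5, correlation 0.6, both stages alike). SE = SD × √(1/20 + 1/21) = 0.3124 × SD.

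- Unadjusted end-of-treatment: SD 5, SE 1.562, ratio 1.92. Power 46.5% by t test; about 48% simulated under the planned model, which has more df.
- Change from baseline: SD 5 × √(2 × 0.4) = 4.47, SE 1.397, ratio 2.15. Power about 55% by t test.
- Baseline-adjusted: SD 5 × √(1 − 0.36) = 4.00, SE 1.250, ratio 2.40. Power about 65%; about 64% simulated.

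The baseline-adjusted contrast held about 5% error in every pattern tried.

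**The case against.** The strongest defence is that the plan is less open than it looks.

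- All three descriptions are mixed models for repeated PCWP, and a random subject effect with default residuals implies compound symmetry. That stands: a structure is implied, though not stated.
- Section 7.4 refers to 3.4, which fixes exercise at 20 W. That largely stands; saying so in 7.6 is a clarification.
- Section 6.1 does not mention feet elevation, but it describes testing by standard practice, so its silence is not a contradiction. That stands.
- The later paragraph of 7.6 points to treatment-by-time terms. That stands too, so it would be wrong to say the documents give no indication of the tested terms. The primary-analysis paragraph should still say it.
- Under the common SD of 5 mmHg used in 7.5, the two-stage end-of-treatment exercise contrast stays at 4.8–5.1% under every correlation pattern tried. That stands, but 7.5 also says the SD grows with the mean. Its example is patients with pulmonary hypertension and not stages, so it sits poorly with equal variances without disproving them.
- In a trial of this size, a heavily parameterised covariance and a changed primary test are debatable, and 7.6 itself worries about convergence. That is a fair limit on the remedy.

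None of this says where a third stage goes in a yes/no factor, or reconciles analysis of covariance with a model that has no covariate.

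**Conclusion.** The inconsistency is established from the text alone: three stages against two, and baseline as covariate against baseline as response. It should be fixed before analysis.

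The numerical consequences are a sensitivity range. A reader might infer that the plan has an inflated type I error of 10% or 15%. The documents do not support that. They give one SD and no variance components, and the departures move the error rate both up and down. A reader might equally infer from the 6–8% range of the 4-df LRT that the primary test is nearly immune. That does not carry over to the 2-df treatment-by-time test that 7.6 seems to intend, which runs from about 1% to about 10%.

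The power gain from about 48% to about 64% assumes a 3 mmHg effect and correlation 0.6, and is against the end-of-treatment contrast; the planned change contrast, if taken at exercise, lies between. At the planned 6 mmHg, the unadjusted t test already has 93.8%, so the gain matters mainly for smaller effects. It comes from baseline adjustment. Stage coding and covariance protect the error rate. The sample-size figure in 7.5 is not wrong.

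**What to change.** 1. Reconcile 3.4 with 7.1, 7.4 and 7.6 on whether feet-elevated PCWP belongs to the endpoint. Code stage with that number of levels, and state that exercise in 7.6 means the 20 W value.
2. State one model in the same words in the Study Summary, 3.4 and 7.6: 24-week PCWP by stage; own-stage baseline PCWP as covariate; treatment, stage and treatment-by-stage; unstructured covariance over stages, with heterogeneous compound symmetry if it does not converge; REML with Kenward-Roger df. A two-visit model with a common baseline mean across arms is an acceptable alternative that keeps baseline-only participants in the model.
3. Name the treatment terms tested and use a small-sample F test for them instead of the chi-square LRT. Report the baseline-adjusted 20 W difference as the key exercise contrast.

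Whether the joint test or the 20 W contrast is primary stays with the sponsor. Section 2 and the 7.5 calculation point to exercise; 3.4 and the Study Summary statistical methodology point to the combined profile.

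**Cost.** Rewording in three places, one reconciliation and a changed form of the primary test; no new data. With three stages, the 24-week model has 3 × 4/2 = 6 covariance parameters, against 6 × 7/2 = 21 for the two-visit alternative. In the 24-week version, participants without a second catheterization contribute no response, and the text should say so in view of the all-available-data commitment. The joint F test may lose some power in some patterns. Its power should be simulated against the treatment-by-time LRT before the text is finalised.
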